### **Purpose and Aims**

The overarching purpose of the suggested research is to investigate the incidence and risk factors as well as long-term complications and consequences of childhood-onset type 1 diabetes (T1D), with an emphasis on understanding the multifactorial aetiology, socioeconomic disparities and gender differences associated with the disease. Through a population-based approach, this research aims to provide evidence for more effective prevention, management, and long-term care strategies for individuals with T1D, while at the same time advancing research methodologies for this and similar chronic conditions. We focus on five main research areas with the following specific aims:

#### **1. Time trends in childhood-onset type 1 diabetes:**

- To examine time, age and cohort effects on the incidence of childhood-onset T1D in Sweden.
- To identify environmental and lifestyle-related risk factors contributing to the increasing incidence of T1D.
- To assess the potential impact of early-life exposures, including pre- and perinatal factors and early childhood infections, on the development of islet autoimmunity and T1D.

#### **2. Diabetic nephropathy and end-stage renal disease:**

- To investigate the incidence, survival and associated risk factors for diabetic nephropathy and end-stage renal disease (ESRD) among individuals with childhood-onset T1D.
- To explore the impact of diabetes management improvements on the declining incidence of ESRD.
- To evaluate sex-specific differences and the influence of pregnancy on the progression of microvascular complications in women with T1D.

#### **3. Socioeconomic circumstances and health outcomes:**

- To examine the impact of familial socioeconomic stress on metabolic control and risk of complications.
- To investigate the long-term health and social outcomes of siblings of individuals with T1D compared to matched controls

#### **4. Health economics and type 1 diabetes:**

- To estimate risk-equations for T1D-related complications and outcomes adapted for use in health-economic models for children, young adults and middle-aged people.
- To analyse consequences of T1D onset in a child on socioeconomic and health-related outcomes for parents.

#### **5. Target trial emulation, case-control studies and time-zero implementation:**

- To develop statistical methods for cohort and case-control designs for setting of “time zero” in target trial emulation for the purpose of assessing causal structures using T1D and various complications as empiric models.

## Survey of the Field

*This is a follow up of a previous grant from the Research Council. Last code: 2018-02565, principal investigator [name].*

### Time Trends in Childhood-onset Type 1 Diabetes

The aetiology of childhood-onset type 1 diabetes (T1D) is multifactorial, arising from a complex interaction between genetic predisposition and environmental risk factors (1,2). In contrast to other autoimmune diseases, T1D predominantly affects younger populations (3). Between 1978 and 2008, the incidence of T1D among children below 15 years in Sweden more than doubled (4). Consequently, alongside asthma, T1D has become one of the most prevalent chronic diseases among children in Sweden. Similar upward trends in incidence have been documented in numerous other countries (5). Over the past decade, the incidence has remained high but stable (Figure 1) (6).

[figure not shown]

Figure 1: The incidence childhood-onset type 1 diabetes in Swedish, foreign and total population 0-15 years divided on boys (a) and girls (b), dots being incidence and lines being predicted incidence from a general additive model (GAM) for Poisson response (6).

The rapid increase in the incidence of childhood-onset T1D can only be attributed to a rise in non-genetic, lifestyle-related risk factors (7). The peak incidence of autoimmunity against insulin-producing  $\beta$ -cells occurs in the second year of life (8), suggesting that environmental triggers likely operate very early, either in utero or during early childhood. A wide range of environmental risk factors have been investigated (2), with several pre- and perinatal factors consistently associated with T1D risk, including maternal obesity, preterm birth, and postnatal growth (9,10). Infections, particularly viral infections, have also been implicated in T1D pathogenesis (11), although their population-level impact is harder to study due to the frequent lack of diagnosis or aetiological identification of childhood infections. Some prospective studies have found associations between respiratory infections and islet autoimmunity (12), whereas others have not (13). During the COVID-19 pandemic, reports indicated an initial rise in T1D incidence followed by a subsequent decline, a trend less pronounced in younger children (14,15). Preliminary data from Sweden suggest similar patterns, though these observations require confirmation through extended follow-up and analysis. A whole-population study in Denmark (16) found no association between SARS-CoV-2 infection and subsequent T1D risk in children, whereas a preliminary report from Norway described a 60% risk increase (17).

### *Significance and Scientific Novelty*

Given the chronic nature of T1D, its severe long-term complications, and the necessity for life-long healthcare, the disease demands increased attention. Continued surveillance of T1D incidence trends is crucial for generating hypotheses on disease aetiology and providing a foundation for future diabetes care and research planning. To better understand the drivers of changing incidence rates, it is essential to link individual-level microdata to population-based variables that could accelerate the pre-existing autoimmune process of T1D. Such variables may be maternal weight, gestational age and postnatal growth.

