### Preliminary and Previous Results

#### Time Trends in Childhood-onset Type 1 Diabetes

The research group has followed childhood-onset T1D incidence since the early 1980s (47). More recently, we have considered trends for a levelling off of the incidence (4) and the impact of demographic dynamics on the incidence trends (6). We have also explored various aetiological risk factors, showing among other things that higher birthweight, moderate prematurity and maternal obesity are independent risk factors for T1D (10).

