#### **Hypothesis 1: The incidence of childhood-onset type 1 diabetes will peak in Sweden during the early 2020s.**

To deepen our knowledge on incidence trends and understand more of age-period and cohort effects in T1D incidence trends, we will make use of hierarchical Age-Period-Cohort (APC) analysis with covariates, see e.g. (60) for a comprehensive overview. Incident cases come from the PDR and covariates will come from the MBR concerning early pregnancy weight and gestational age and from the CHS regarding child growth (61). We will expand our previous analysis using non-linear semiparametric generalized additive models for count data (4,6). The time related changes we study are age effects (A), period effects (P) and shared life events for a set of individuals, i.e., cohort effects (C). The fitted APC models can be evaluated with model diagnostics and give (i) the magnitude of the individual APC effects. For example, the minimum and maximum values of the marginal APC effects and the overall size of each effect, (ii) an assessment of one-dimensional covariate smooth effects, for example for child weight or mother's weight respectively, and (iii) a table with full model results. Either a list of several models or for a single model, here both linear coefficients and all nonlinear estimates are returned. The work will resume during the latter part of the period, with IW and TL leading.

---

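### Hypothesis 1 names early pregnancy weight as the maternal covariate although the rationale is maternal obesity; entered without height, weight does not estimate the obesity association

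*Protocol*

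**What the plan says.** The rationale is about obesity. The background section on time trends refers to "several pre- and perinatal factors consistently associated with T1D risk, including maternal obesity, preterm birth, and postnatal growth". Under preliminary and previous results, the group reports its own finding that "higher birthweight, moderate prematurity and maternal obesity are independent risk factors for T1D".

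The variable proposed for analysis is weight. The significance section that follows the background says, tentatively, "Such variables may be maternal weight, gestational age and postnatal growth". The operative text is the project description for Hypothesis 1, which states that "covariates will come from the MBR concerning early pregnancy weight and gestational age and from the CHS regarding child growth". Among the outputs of the fitted age-period-cohort models it lists "an assessment of one-dimensional covariate smooth effects, for example for child weight or mother's weight respectively".

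The specific aim that these covariates serve is "To identify environmental and lifestyle-related risk factors contributing to the increasing incidence of T1D".

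Maternal height, BMI and an obesity category appear nowhere in the Protocol. Nor does it say that height will be left out.

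**The concern.** The factor that motivates the analysis and the covariate named for it are not the same quantity. Weight is BMI multiplied by height squared, so a smooth of weight alone places a tall woman of normal BMI beside a short woman with obesity. Obesity is the part of weight that fits an aim about lifestyle-related risk factors; stature is not.

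What is at stake is how the maternal result can be read. A smooth of weight alone could not be set directly against the group's earlier maternal-obesity result, and it would not show how strongly obesity itself is associated with incidence. Height might also be related to the outcome by other routes, for example through child growth, which is in the same model. The Protocol gives nothing from which to judge that.

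**Working it through.** The Protocol states no effect size, power or variance for a maternal covariate, so there is no figure of its own to reproduce. The check has three parts.

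**1. The texts side by side**

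| Place in the Protocol | Maternal variable |
|---|---|
| Background, time trends | obesity |
| Previous results, time trends | obesity |
| Significance, time trends | weight (tentative) |
| Hypothesis 1, covariate sentence | early pregnancy weight |
| Hypothesis 1, example output | mother's weight |

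The rationale uses obesity both times. The three places that look ahead to the analysis use weight each time.

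**2. What weight alone can and cannot separate**

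BMI = weight / height². This is arithmetic on chosen values:

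- At 75 kg, BMI is 75 / 1.58² = 30.0 at 158 cm, 75 / 1.74² = 24.8 at 174 cm, and 75 / 1.80² = 23.1 at 180 cm.
- A BMI of 30 corresponds to 30 × 1.55² = 72 kg at 155 cm and 30 × 1.80² = 97 kg at 180 cm.

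**3. Illustrative size**

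None of these inputs is in the Protocol; all are assumptions.

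- SD of log-BMI: 0.12 to 0.20.
- SD of log-height: 0.035 to 0.042. The upper value is a height SD of 7 cm at a mean of 166 cm, 7 / 166 = 0.042.
- BMI is independent of height, and height has no effect of its own.

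Since ln(weight) = ln(BMI) + 2 ln(height), the slope on ln(weight) equals the slope on ln(BMI) multiplied by

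factor = s²(BMI) / [s²(BMI) + 4 s²(height)].

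| SD log-BMI | SD log-height | Factor | Attenuation |
|---|---|---|---|
| 0.20 | 0.035 | 0.0400 / (0.0400 + 0.0049) = 0.89 | 11% |
| 0.17 | 0.036 | 0.85 | 15% |
| 0.17 | 0.042 | 0.80 | 20% |
| 0.12 | 0.040 | 0.0144 / (0.0144 + 0.0064) = 0.69 | 31% |
| 0.12 | 0.042 | 0.67 | 33% |

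The square root of the factor is the correlation between log-weight and log-BMI, here about 0.82 to 0.94. On these assumptions weight is a usable but imperfect proxy.

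A simulation of 2 million women shows the same in terms of ranking. It adds an assumed median BMI of 24 and uses a mean height of 166 cm with an SD of 6 to 7 cm. The share of women with BMI 30 or more who fall outside the equally large top-weight group is 22% to 25% at a log-BMI SD of 0.20, 28% to 32% at 0.17, and 46% to 51% at 0.12.

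**The case against.** The strongest reply is that the absence of height is inferred from silence. The significance section is motivation and is hedged. The Hypothesis 1 text gives mother's weight only as an example of an output, not as a closed covariate list, and a one-dimensional smooth of weight does not rule out a separate height term. The same paragraph moves between child growth and child weight, so weight may be shorthand for weight status. How a covariate is coded is commonly left to the statistical analysis plan, which is not at hand.

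Part of this stands. The point has to be conditional on weight being entered without height, and it is no more than minor. It does not dispose of the mismatch. The Hypothesis 1 text goes beyond leaving the coding open: it names the register, the variable and its timing, and repeats weight in the output list. That is a stated choice, and it differs from the rationale.

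Two stronger readings are tempting, and the Protocol supports neither:

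- A reader might infer that the plan misstates the contribution of obesity to incidence. It promises neither an obesity effect nor an attributable share, and a weight effect reported as a weight effect misstates nothing.
- A reader might infer that the weight smooth is confounded by population origin, because the background figure splits incidence into Swedish and foreign population. The Protocol does not say that maternal height differs between these groups, nor that origin will be left out of the model.

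The numerical illustration is also open to challenge. It compares linear slopes on the log scale, whereas the plan is for non-linear smooths.

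**Conclusion.** The point holds in conditional form. The maternal covariate named for Hypothesis 1 is not the risk factor that motivates it. If weight is entered without height, as the text reads, the resulting smooth mixes adiposity with stature and does not estimate the obesity association.

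An attenuation of roughly 11% to 33% is an order of magnitude only. It rests on assumed spreads of BMI and height, on their independence, and on a log-linear effect. Quoting 15% to 20% would be too narrow, because that range fixes the log-BMI SD at 0.17. Neither the direction nor the size of any confounding by height can be determined from the Protocol.

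Severity is minor: a cheap improvement to a stated variable choice, not a demonstrated error in a result.

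**What to change.** In the Hypothesis 1 text, replace early pregnancy weight by early-pregnancy BMI, or keep weight and enter maternal height beside it. Name that smooth as the maternal output in place of the smooth of mother's weight. Change the significance section on time trends in the same way so that the two agree. If only weight is available, say so, and report the result as a weight effect and not as an obesity effect.

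The cost is one derived variable (or one extra covariate) and a wording change. Records without height would be lost or would need imputation. That height is available is an assumption; the group's earlier maternal-obesity result makes it likely, but it should be confirmed.

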### **Diabetic Nephropathy and End-Stage Renal Disease**

Diabetic nephropathy is the most severe long-term complication of T1D, leading to glomerulosclerosis, progressive glomerular dysfunction, and ultimately ESRD. This life-threatening condition necessitates renal replacement therapy (RRT) via dialysis or transplantation. Diabetic nephropathy is also a key contributor to premature mortality in T1D, driving both renal failure and cardiovascular disease risk (18). A meta-analysis demonstrated increased cardiovascular and all-cause mortality in diabetes patients, although mortality risk among those with chronic kidney disease was comparable irrespective of diabetes status (24), which emphasizes the importance of renal disease. Our research group previously reported that T1D accounted for 10% of ESRD cases, later decreasing to 5.6%, potentially reflecting improved diabetes management, hypertension, and dyslipidaemia control (19,20). Finnish data also indicated a declining ESRD incidence, with onset typically 15 years post-T1D diagnosis, peaking at 25 years before plateauing (21). However, it remains unclear whether current interventions genuinely reduce risk or merely delay nephropathy progression.

Epidemiological studies show varying nephropathy incidence across populations (22), disproportionately affecting socioeconomically disadvantaged individuals (23,24). Survival after RRT onset depends on treatment modality and socioeconomic status, highlighting disparities in healthcare access and outcomes (25).

Sex differences in nephropathy risk remain inconsistent. While men appear at higher risk than premenopausal women, postmenopausal women show increased susceptibility. Age at diabetes onset may further influence this risk (26). Among women with T1D, pregnancy outcomes are closely linked to glycaemic control, with poor metabolic control increasing maternal and foetal morbidity and mortality; however, the long-term impact of pregnancy on complications such as nephropathy progression remains understudied, despite that evidence-based guidance could have a significant impact on pregnancy strategies for all T1D women (27).

### *Significance and Scientific Novelty*

Continuous monitoring of ESRD trends concerning socioeconomic factors, comorbidities, and RRT modalities is vital to understanding this serious complication. Exploring pregnancy as a novel risk factor for diabetic nephropathy will enhance knowledge of gender differences in T1D outcomes.

### **Socioeconomic Circumstances and Health Outcomes**

Type 1 diabetes management requires strict adherence to insulin therapy and blood glucose monitoring (28). Socioeconomic stress, particularly in families with low income or parental edu-

cation, has been linked to increased risks of long-term complications, including nephropathy and premature mortality in adulthood (29,30). Socioeconomically disadvantaged children with T1D also exhibit poorer metabolic control (31); however, whether this persists into adulthood remains debated, as systematic reviews report conflicting results (32).

A T1D diagnosis affects the entire family, inducing distress in parents and siblings (33). While siblings develop coping mechanisms, their emotional needs may be underestimated, leading to increased rates of depression and anxiety (34). Previous research has primarily examined the immediate post-diagnosis period, often with small sample sizes and short follow-up durations (35). Our prior findings indicate that brothers of individuals with T1D, but not sisters, have lower annual earnings compared to their peers (36), yet the long-term health consequences for siblings are largely unexplored.

#### *Significance and Scientific Novelty*

Understanding T1D in a life course perspective requires examining the relationship between childhood socioeconomic status and long-term glycaemic control. Further research into mortality, hospitalisations, and mental health outcomes among T1D siblings compared to matched controls is essential for comprehensively addressing the broader impacts of T1D on affected families.

#### **Health Economics and Type 1 Diabetes**

Health-economic evaluation models in diabetes, typically microsimulations or Markov models (37), rely on risk equations that capture short- and long-term outcomes influenced by interventions such as improved diagnostics and treatment (38–40). These models link health outcomes to costs and patient benefits, aiding healthcare decision-making and guideline optimisation. Traditionally, models for T1D have been based on the American Diabetes Control and Complications Trial (DCCT) (41), and its follow-up, the Epidemiology of Diabetes Interventions and Complications (EDIC) study (42), alongside frameworks borrowed from Type 2 Diabetes, despite fundamental differences in aetiology, onset and risk factors.

There is a growing need to refine models for T1D evaluation (39,40), including the integration of risk equations derived from more recent patient cohorts, such as Swedish observational data (40). Existing health-economic models predominantly focus on adult populations and long-term vascular complications, with limited data available on children and adolescents. Additionally, mental health effects (43) and other non-vascular complications remain underrepresented. While international research on T1D complications is expanding, it tends to be clinically focused and lacks straightforward applicability to health-economic models.

Understanding the short- and long-term consequences of T1D across the lifespan is increasingly important due to advances in early risk identification, interventions to reduce incidence (44) (GPPAD-POInT at ClinicalTrials.gov IDNCT03364868), and discussions on newborn screening. In this context, health-economic models will support decision-makers in assessing the value of delaying T1D onset in terms of patient outcomes and cost savings.

#### *Significance and Scientific Novelty*

There is a critical need for updated risk estimates of T1D complications that can be integrated into health-economic simulation models. Such models are essential for researchers to assess

new interventions and for organisations that evaluate treatments and diagnostics, including Health-Technology Assessment agencies and the life sciences industry. While existing models primarily address micro- and macrovascular complications that typically arise after age 50, future models should incorporate risk estimates for T1D-related outcomes affecting children, adolescents, and younger adults, as well as the caregiving burden on parents of children with T1D.

### Target Trial Emulation, Case-Control Studies and Time-zero Implementation

Observational studies are increasingly designed to emulate randomised controlled trials (RCTs) to strengthen causal inference, a concept known as Target Trial Emulation (TTE) (45). RCTs remain the gold standard for causal effect estimation due to their ability to eliminate confounding and simplify analyses. However, well-structured observational studies can provide valuable insights by incorporating key RCT elements such as eligibility criteria, treatment assignment, randomisation, and clearly defined "time zero" for follow-up. In Hernán et al. (46) four examples are given of failures to emulate a target trial using observational data (Figure 2).

[figure not shown]

Figure 2. Four examples of failures of emulation of a target trial using observational data. Here,  $T_0$  is time zero, E is eligibility, and A is a period under which treatments are assigned (46).

### Significance and Scientific Novelty

The significance of TTE continues to grow within epidemiological and statistical research. Advancing this framework necessitates new case-control study designs that can be practically applied by data analysts. Further methodological development is required to refine observational study designs to more closely resemble RCTs.

### Preliminary and Previous Results

#### Time Trends in Childhood-onset Type 1 Diabetes

The research group has followed childhood-onset T1D incidence since the early 1980s (47). More recently, we have considered trends for a levelling off of the incidence (4) and the impact of demographic dynamics on the incidence trends (6). We have also explored various aetiological risk factors, showing among other things that higher birthweight, moderate prematurity and maternal obesity are independent risk factors for T1D (10).

